7.2.3.2 Events of Clinical Interest

Selected non-serious and serious adverse events are also known as Events of Clinical Interest (ECI) and must be reported to the Sponsor.

For the time period beginning when the consent form is signed until treatment allocation/randomization, any ECI, or follow up to an ECI, that occurs to any subject must be reported within 24 hours to the Sponsor if it causes the subject to be excluded from the trial, or is the result of a protocol-specified intervention, including but not limited to washout or discontinuation of usual therapy, diet, placebo treatment or a procedure.

For the time period beginning at treatment allocation/randomization through 14 days following cessation of treatment, any ECI, or follow up to an ECI, whether or not related to the Sponsor's product, must be reported within 24 hours to the Sponsor, either by electronic media or paper. Electronic reporting procedures can be found in the EDC data entry guidelines. Paper reporting procedures can be found in the Investigator Trial File Binder (or equivalent). Events of clinical interest for this trial include:

1. an overdose of Sponsor's product, as defined in Section 7.2.1 - Definition of an Overdose for This Protocol and Reporting of Overdose to the Sponsor, that is not associated with clinical symptoms or abnormal laboratory results.
2. an elevated AST or ALT lab value that is greater than or equal to 3X the upper limit of normal and an elevated total bilirubin lab value that is greater than or equal to 2X the upper limit of normal and, at the same time, an alkaline phosphatase lab value that is less than 2X the upper limit of normal, as determined by way of protocol-specified laboratory testing or unscheduled laboratory testing.*

*Note: These criteria are based upon available regulatory guidance documents. The purpose of the criteria is to specify a threshold of abnormal hepatic tests that must trigger an additional evaluation for an underlying etiology. The trial site guidance for assessment

and follow up of these criteria can be found in the Investigator Trial File Binder (or equivalent).

It may also be appropriate to conduct additional evaluation for an underlying etiology in the setting of abnormalities of liver blood tests including AST, ALT, bilirubin, and alkaline phosphatase that do not meet the criteria noted above. In these cases, the decision to proceed with additional evaluation will be made through consultation between the study investigators and the Sponsor Clinical Director. However, abnormalities of liver blood tests that do not meet the criteria noted above are not ECIs for this trial.

7.2.4 Evaluating Adverse Events

An investigator who is a qualified physician will evaluate all adverse events with respect to the elements outlined in Table 7. The investigator's assessment of causality is required for each adverse event. Refer to Table 7 for instructions in evaluating adverse events.

Table 7 Evaluating Adverse Events

Maximum Intensity	Mild	awareness of sign or symptom, but easily tolerated (for pediatric trials, awareness of symptom, but easily tolerated)
	Moderate	discomfort enough to cause interference with usual activity (for pediatric trials, definitely acting like something is wrong)
	Severe	incapacitating with inability to work or do usual activity (for pediatric trials, extremely distressed or unable to do usual activities)
Seriousness	A serious adverse event (AE) is any adverse event occurring at any dose or during any use of Sponsor's product that:	
	† Results in death ; or	
	† Is life threatening ; or places the subject, in the view of the investigator, at immediate risk of death from the event as it occurred [Note: This does not include an adverse event that, had it occurred in a more severe form, might have caused death.]; or	
	† Results in a persistent or significant disability/incapacity (substantial disruption of one's ability to conduct normal life functions); or	
	† Results in or prolongs an existing inpatient hospitalization (hospitalization is defined as an inpatient admission, regardless of length of stay, even if the hospitalization is a precautionary measure for continued observation. (Note: Hospitalization for an elective procedure to treat a pre-existing condition that has not worsened is not a serious adverse event. A pre-existing condition is a clinical condition that is diagnosed prior to the use of a Merck product and is documented in the patient's medical history.); or	
	† Is a congenital anomaly/birth defect (in offspring of subject taking the product regardless of time to diagnosis); or	
	Is a cancer (although not serious per ICH definition, is reportable to the Sponsor within 24 hours to meet certain local requirements); or	
	Is associated with an overdose (whether accidental or intentional). Any adverse event associated with an overdose is considered a serious adverse event for collection purposes. An overdose that is not associated with an adverse event is considered a non-serious event of clinical interest and must be reported within 24 hours.	
Other important medical events that may not result in death, not be life threatening, or not require hospitalization may be considered a serious adverse event when, based upon appropriate medical judgment, the event may jeopardize the subject and may require medical or surgical intervention to prevent one of the outcomes listed previously (designated above by a †).		
Duration	Record the start and stop dates of the adverse event. If less than 1 day, indicate the appropriate length of time and units	
Action taken	Did the adverse event cause the Sponsor's product to be discontinued?	
Relationship to Sponsor's Product	Did the Sponsor's product cause the adverse event? The determination of the likelihood that the Sponsor's product caused the adverse event will be provided by an investigator who is a qualified physician. The investigator's signed/dated initials on the source document or worksheet that supports the causality noted on the AE form, ensures that a medically qualified assessment of causality was done. This initialed document must be retained for the required regulatory time frame. The criteria below are intended as reference guidelines to assist the investigator in assessing the likelihood of a relationship between the test drug and the adverse event based upon the available information	
	The following components are to be used to assess the relationship between the Sponsor's product and the AE ; the greater the correlation with the components and their respective elements (in number and/or intensity), the more likely the Sponsor's product caused the adverse event:	
	Exposure	Is there evidence that the subject was actually exposed to the Sponsor's product such as: reliable history, acceptable compliance assessment (pill count, diary, etc.), expected pharmacologic effect, or measurement of drug/metabolite in bodily specimen?
	Time Course	Did the AE follow in a reasonable temporal sequence from administration of the Sponsor's product? Is the time of onset of the AE compatible with a drug-induced effect (applies to trials with investigational medicinal product)?
Likely Cause	Is the AE not reasonably explained by another etiology such as underlying disease, other drug(s)/vaccine(s), or other host or environmental factors	

Relationship to Sponsor's Product (continued)	The following components are to be used to assess the relationship between the Sponsor's product and the AE: (continued)	
	Dechallenge	Was the Sponsor's product discontinued or dose/exposure/frequency reduced? If yes, did the AE resolve or improve? If yes, this is a positive dechallenge. If no, this is a negative dechallenge. (Note: This criterion is not applicable if: (1) the AE resulted in death or permanent disability; (2) the AE resolved/improved despite continuation of the Sponsor's product; (3) the trial is a single-dose drug trial); or (4) Sponsor's product(s) is/are only used one time.)
	Rechallenge	Was the subject re-exposed to the Sponsor's product in this trial? If yes, did the AE recur or worsen? If yes, this is a positive rechallenge. If no, this is a negative rechallenge. (Note: This criterion is not applicable if: (1) the initial AE resulted in death or permanent disability, or (2) the trial is a single-dose drug trial); or (3) Sponsor's product(s) is/are used only one time.) NOTE: IF A RECHALLENGE IS PLANNED FOR AN ADVERSE EVENT WHICH WAS SERIOUS AND WHICH MAY HAVE BEEN CAUSED BY THE SPONSOR'S PRODUCT, OR IF RE-EXPOSURE TO THE SPONSOR'S PRODUCT POSES ADDITIONAL POTENTIAL SIGNIFICANT RISK TO THE SUBJECT THEN THE RECHALLENGE MUST BE APPROVED IN ADVANCE BY THE SPONSOR CLINICAL DIRECTOR AND THE INSTITUTIONAL REVIEW BOARD/INDEPENDENT ETHICS COMMITTEE.
	Consistency with Trial Treatment Profile	Is the clinical/pathological presentation of the AE consistent with previous knowledge regarding the Sponsor's product or drug class pharmacology or toxicology?
The assessment of relationship will be reported on the case report forms /worksheets by an investigator who is a qualified physician according to his/her best clinical judgment, including consideration of the above elements.		
Record one of the following:	Use the following scale of criteria as guidance (not all criteria must be present to be indicative of a Sponsor's product relationship).	
Yes, there is a reasonable possibility of Sponsor's product relationship.	There is evidence of exposure to the Sponsor's product. The temporal sequence of the AE onset relative to the administration of the Sponsor's product is reasonable. The AE is more likely explained by the Sponsor's product than by another cause.	
No, there is not a reasonable possibility of Sponsor's product relationship	Subject did not receive the Sponsor's product OR temporal sequence of the AE onset relative to administration of the Sponsor's product is not reasonable OR the AE is more likely explained by another cause than the Sponsor's product. (Also entered for a subject with overdose without an associated AE.)	

7.2.5 Sponsor Responsibility for Reporting Adverse Events

All Adverse Events will be reported to regulatory authorities, IRB/IECs and investigators in accordance with all applicable global laws and regulations, i.e., per ICH Topic E6 (R1) Guidelines for Good Clinical Practice.

8.0 STATISTICAL ANALYSIS PLAN

8.1 Statistical Analysis Plan Summary

8.1.1 Source of Variance Estimates: Precision and Sample Size

The sample size selected for each population to evaluate the effect of HI on the PK of MK-3866 was not chosen to satisfy any a priori statistical requirement. This sample size (N=6 per group) has historically been shown to be sufficient for studies of this type and should provide adequate data to support the planned analyses. Nevertheless, estimates of the expected precision of the estimates based on these sample sizes are presented below.

The precision of the estimates of ratios of geometric means obtained from this study can be assessed by calculating the half-width of the 90% confidence intervals expected for the given sample size and assumed variability. The estimated between-subject variance for log AUC_{0-∞} is 0.0196 log ng•hr/mL from a previous study (PN001). Since the between subject variability in severe hepatic insufficient subjects is usually higher in many studies, the between subject variability obtained from healthy were inflated by a factor of 2 for severe hepatic insufficient subjects and was used for the following calculations. With 6 hepatic insufficient subjects and 6 healthy matched subjects, the half-width of the 90% confidence interval for the arithmetic mean AUC_{0-∞} on the log scale will be 0.179 log ng•hr/mL. The lower and upper 90% confidence limits for the true ratio of geometric means will be given by OBS/1.163 and OBS x 1.197, where OBS is the observed ratio of geometric means. Thus, for example, if the observed ratio of geometric means was 1.5, the 90% confidence interval would be (1.25, 1.79).

8.1.2 Statistical Core Methods:

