8.1.2.1 Primary PK Analysis

Separately for each pharmacokinetic parameter, individual values of AUC_{0-∞}, AUC_{0-last}, AUC₀₋₂₄, C_{eo}, and CL will be natural log-transformed and evaluated with a linear fixed effects model containing a categorical effect for populations. The REPEATED statement with the GROUP=Population option will be used in SAS PROC MIXED to estimate separate variances for each population. The Kenward and Roger adjustment will be used to calculate the denominator degrees of freedom for the fixed-effect (DDFM=KR). Ninety-five percent (95%) confidence intervals for the least squares means for each population will be constructed on the natural log scale and will reference the t-distribution. Exponentiating the least-squares means and their corresponding 95% confidence intervals will yield estimates for the population geometric means and confidence intervals about the geometric means on the original scale.

To compare subjects with HI in each of the hepatic insufficient categories (moderate HI and severe HI) to matching subjects with normal hepatic function, a two sided 90% confidence interval for the true difference in means (HI – normal hepatic function) will be calculated for each PK parameters (AUC_{0-∞}, AUC_{0-last}, AUC₀₋₂₄, C_{ei}, and CL) using the mean square error from the model and referencing a t-distribution. For each of the HI populations, these confidence limits will be exponentiated to obtain the 90% confidence interval for the true ratio of geometric means (HI/normal hepatic function) for each pharmacokinetic parameter.

Figures showing individual pharmacokinetic values with GMs (95% confidence intervals) by population, plotted on the natural log scale, will be provided for AUC_{0-∞}, AUC_{0-last}, AUC₀₋₂₄, C_{ei}, and CL.

Individual values will be listed for each PK parameter (AUC_{0-∞}, AUC_{0-last}, AUC₀₋₂₄, C_{ei}, T_{max}, CL, V_z, and apparent terminal t_{1/2}) by population, and the following (non model-based) descriptive statistics will be provided: N (number of subjects with non-missing data), arithmetic mean, standard deviation, arithmetic percent CV (calculated as 100 x standard deviation/arithmetic mean), median, minimum, maximum, geometric mean, and geometric percent CV (calculated as 100 x sqrt(exp(s₂) - 1), where s₂ is the observed variance on the natural log-scale).

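### Section 8.1.1 prints a lower-limit divisor of 1.163; the SAP's own half-width, upper factor and worked example all require about 1.197

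*Combined protocol and SAP*

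**What the plan says.** Section 8.1.1 states that the sample size "was not chosen to satisfy any a priori statistical requirement" and then gives the precision to be expected. The between-subject variance of log AUC0-inf is 0.0196, from PN001. For severe hepatic impairment this is "inflated by a factor of 2 for severe hepatic insufficient subjects". The SAP continues: "With 6 hepatic insufficient subjects and 6 healthy matched subjects", "the half-width of the 90% confidence interval for the arithmetic mean" AUC0-inf on the log scale is 0.179. The lower and upper 90% limits for the ratio "will be given by OBS/1.163 and OBS x 1.197", where OBS is the observed ratio. The section closes with an example: "if the observed ratio of geometric means was 1.5, the 90% confidence interval would be (1.25, 1.79").

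Section 8.1.2.1 describes how the interval is formed. A two-sided 90% t-interval is calculated for the difference in log means, and "these confidence limits will be exponentiated to obtain the 90% confidence interval for the true ratio of geometric means". The same section fits the model so as "to estimate separate variances for each population".

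**The concern.** A t-interval for a difference in log means has the form d ± h. Exponentiating it gives OBS/exp(h) and OBS × exp(h), so the divisor and the multiplier are one number. The SAP prints two, 1.163 and 1.197, for a single half-width.

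This is the SAP's only statement of expected precision, and it concerns AUC0-inf, the parameter named in both primary estimations in Section 3.1. The formula is what a reader would use to judge precision at a ratio other than the 1.5 of the example. With the printed divisor the lower side of the interval looks tighter than the stated variance and group sizes allow.

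The wording beside it is also loose. It attaches 0.179 to a mean, whereas the figure is for a difference between two groups' means of log AUC0-inf.

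**Working it through.** **Inputs**
- Variance of log AUC0-inf in healthy subjects: 0.0196 (Section 8.1.1).
- Variance in severe hepatic impairment: 2 × 0.0196 = 0.0392 (Section 8.1.1).
- Group sizes: 6 and 6 (Section 8.1.1).
- Two-sided 90% interval with a t reference (Section 8.1.2.1).
- Degrees of freedom: not stated for this calculation. I assume 6 + 6 − 2 = 10, which reproduces the SAP's half-width.

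**Reproducing the SAP's figures**
- SE of the difference = sqrt((0.0196 + 0.0392)/6) = 0.0990.
- h = t(0.95, 10 df) × SE = 1.8125 × 0.0990 = 0.1794, printed as 0.179.
- exp(h) = 1.1965, printed as 1.197.
- At OBS = 1.5: 1.5/1.1965 = 1.254 and 1.5 × 1.1965 = 1.795 (unrounded 1.7948), printed as 1.25 and 1.79.

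The half-width, the upper factor and both example limits therefore agree with the stated inputs. The upper limit of 1.79 is not an error. Multiplying by the rounded factor gives 1.5 × 1.197 = 1.7955, which would print as 1.80, but the unrounded 1.7948 prints as 1.79.

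**Testing the divisor against the figures beside it**
- Against the half-width: ln(1.163) = 0.151, not 0.179. The shortfall is 1 − 0.151/0.179 = 15.6%. A half-width printed as 0.179 lies between 0.1785 and 0.1795, which allows only factors from 1.195 to 1.197.
- Against the example: 1.5/1.163 = 1.290, but 1.25 is printed. A lower limit that rounds to 1.25 needs a divisor between 1.5/1.255 = 1.195 and 1.5/1.245 = 1.205, so rounding cannot explain 1.163.
- With 1.197 in its place: 1.5/1.197 = 1.253, which prints as 1.25.

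**Size of the error**
- 1.197/1.163 = 1.029, so the lower limit is 2.9% too high at every observed ratio.
- At OBS = 2.0: 2.0/1.163 = 1.72 against 2.0/1.197 = 1.67.

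**Could 1.163 belong to another calculation?** These are the closest plausible variants.

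| Variant | Half-width | Factor |
|---|---|---|
| Variance doubled in severe group, separate variances, Satterthwaite 9 df | 0.1815 | 1.199 |
| No inflation in either group (as for moderate impairment), 10 df | 0.1465 | 1.158 |
| Variance doubled in severe group, normal quantile | 0.1628 | 1.177 |
| Variance doubled in both groups, 10 df | 0.2072 | 1.230 |

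None of the variants tried gives 1.163. The nearest, 1.158, would also contradict the 0.179 and the 1.197 printed with it.

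**The case against.** The strongest reply is that nothing depends on this number. The SAP says the sample size was not set to meet a statistical requirement, and offers the precision figures only for information. The confidence intervals in Section 8.1.2.1 will be computed from the trial data, so neither 1.163 nor 1.197 enters any analysis, and no decision rule is attached to the lower limit. The correct lower limit stands in the next sentence, so a reader who tries the formula on the example will see the mismatch. All of this stands, and it limits the point to a minor one. It does not make the printed divisor correct.

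The loose description of 0.179 can also be defended. The paragraph opens by speaking of ratios of geometric means, the sentence names both groups, and the limits that follow are for a ratio. The meaning can be recovered, so this part is editorial.

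Finally, 1.197 is not exactly the factor for the planned model. With separate variances and about 9 df the factor is 1.199. That is true, but the difference is small, and 1.197 is the value that agrees with the half-width, upper factor and example already printed.

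**Conclusion.** The divisor 1.163 is wrong. This follows from Section 8.1.1's own half-width, upper factor and worked example, together with the log-scale symmetry of the interval in Section 8.1.2.1, and needs no outside figure. As printed, it sets the lower limit 2.9% too high at any ratio (1.29 instead of 1.25 at 1.5) and implies a lower half-width of 0.151 instead of 0.179. Sample size, analysis and conduct are unaffected, so the severity is minor.

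The contradiction itself rests on no assumption. Two inferences enter only the reconstruction of 0.179: that 10 df were used, and that the figure refers to severe impairment, the group for which the doubled variance is stated. Both are supported by the fact that together they reproduce the half-width, the upper factor and the example.

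**What to change.** In Section 8.1.1:
- Change the lower limit from OBS/1.163 to OBS/1.197.
- Describe 0.179 as the half-width of the 90% confidence interval for the difference in mean log AUC0-inf between severe hepatic impairment and matched controls (6 v 6, variances 0.0392 and 0.0196). Stating the 10 df, once the sponsor has confirmed it, would let a reader check the figure.
- Leave the example interval of 1.25 to 1.79 as it is.

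The cost is one number and one descriptive phrase in the SAP text. Sample size, analysis and conduct do not change.

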8.1.2.1 Primary PK Analysis

Separately for each pharmacokinetic parameter, individual values of AUC_{0-∞}, AUC_{0-last}, AUC₀₋₂₄, C_{eo}, and CL will be natural log-transformed and evaluated with a linear fixed effects model containing a categorical effect for populations. The REPEATED statement with the GROUP=Population option will be used in SAS PROC MIXED to estimate separate variances for each population. The Kenward and Roger adjustment will be used to calculate the denominator degrees of freedom for the fixed-effect (DDFM=KR). Ninety-five percent (95%) confidence intervals for the least squares means for each population will be constructed on the natural log scale and will reference the t-distribution. Exponentiating the least-squares means and their corresponding 95% confidence intervals will yield estimates for the population geometric means and confidence intervals about the geometric means on the original scale.

To compare subjects with HI in each of the hepatic insufficient categories (moderate HI and severe HI) to matching subjects with normal hepatic function, a two sided 90% confidence interval for the true difference in means (HI – normal hepatic function) will be calculated for each PK parameters (AUC_{0-∞}, AUC_{0-last}, AUC₀₋₂₄, C_{ei}, and CL) using the mean square error from the model and referencing a t-distribution. For each of the HI populations, these confidence limits will be exponentiated to obtain the 90% confidence interval for the true ratio of geometric means (HI/normal hepatic function) for each pharmacokinetic parameter.

Figures showing individual pharmacokinetic values with GMs (95% confidence intervals) by population, plotted on the natural log scale, will be provided for AUC_{0-∞}, AUC_{0-last}, AUC₀₋₂₄, C_{ei}, and CL.

Individual values will be listed for each PK parameter (AUC_{0-∞}, AUC_{0-last}, AUC₀₋₂₄, C_{ei}, T_{max}, CL, V_z, and apparent terminal t_{1/2}) by population, and the following (non model-based) descriptive statistics will be provided: N (number of subjects with non-missing data), arithmetic mean, standard deviation, arithmetic percent CV (calculated as 100 x standard deviation/arithmetic mean), median, minimum, maximum, geometric mean, and geometric percent CV (calculated as 100 x sqrt(exp(s₂) - 1), where s₂ is the observed variance on the natural log-scale).

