4.2 Rationale

4.2.1 Rationale for the Trial and Selected Subject Population

MK-3866 is being developed for use

[REDACTED]

[REDACTED] Gram-negative bacteria. MK-3866 has recently completed dosing the first-in-human (FIH) single ascending dose study (PN001).

The primary purpose of this study is to understand the effect of HI on the plasma PK of MK-3866 in order to guide dosing recommendations for patients with HI. As a proportion of patients with serious Gram-negative infections have baseline HI, it is important to evaluate the impact of HI on the plasma PK of MK-3866. This study will also evaluate the safety and tolerability of MK-3866 in subjects with moderate and severe HI.

Renal clearance is expected to be the major elimination pathway for MK-3866, as approximately 65% of MK-3866 is excreted in the urine following a single IV dose. Based on preclinical animal studies, hepatic elimination is anticipated to be a significant elimination pathway for MK-3866 as well and is expected to account for the remainder of the non-renal elimination of MK-3866, approximately 35%. MK-3866 is also a substrate for the liver specific transporters human organic anion transporting polypeptide (OATP) 1B1/SLCO1B1 (OATP1B1) and OATP1B3. Conducting a dedicated hepatic study for MK-3866 is in line with regulatory guidance which suggests a dedicated hepatic study be conducted for compounds in which hepatic elimination exceeds 20%.

In the FIH study of MK-3866 in healthy subjects, while single and divided doses of up to 2000 mg were generally well-tolerated, nausea was observed with an increased frequency at single doses above 800 mg. In each case, nausea was transient and its onset appeared to coincide temporally with the peak plasma concentration (although the relationship between PK and the development of nausea is currently under investigation).

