It is predicted that the potential effect of HI on single-dose PK will be to reduce the clearance, thereby increasing the terminal half-life and AUC of MK-3866. It is assumed that there is generally a linear relationship between the effect on $t_{1/2}$ and AUC. Based on PN001, approximately 35% of MK-3866 may be hepatically eliminated; exposure increases with severe HI are anticipated to be approximately 1.5-fold. However, it is difficult to provide estimates for hepatic impairment; there is no single accepted measure to use in order to determine PK estimations for varying degrees of liver impairment. In consideration of both the PK and the tolerability of MK-3866 in subjects with HI, the dose of study drug in this trial was selected so that the exposure in all subjects should not exceed 800 mg in healthy subjects (AUC_{0-inf} of 272 $\mu\text{M}\cdot\text{hr}$ and C_{eo} of 97 μM), and is unlikely to exceed the exposure at 400 mg (2.7-fold higher than the 150 mg dose) in healthy subjects (AUC_{0-inf} of 147 $\mu\text{M}\cdot\text{hr}$ and C_{eo} of 52 μM). On the basis of these predicted exposures from a single 150 mg dose of MK-3866 in subjects with either moderate or severe HI, both panels can be recruited in parallel without posing a risk to subject safety.

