8.1.2.2 Secondary PK Analysis

8.1.2.2.1 Objective 1

Separately for each urine pharmacokinetic parameter, individual values of fe and CL_r will be natural log-transformed and evaluated with a linear fixed effects model, which is described in the primary analysis. Ninety-five percent (95%) confidence intervals for the least squares means for each population will be constructed. To compare subjects with HI in each of the hepatic insufficient categories (moderate HI and severe HI) to matching subjects with normal hepatic function, a two sided 90% confidence interval for the true difference in means (HI – normal hepatic function) will be calculated for each urine PK parameters (fe and CL_r).

Individual values will be listed for each urine PK parameter (fe and CL_r) by population, and non model-based descriptive statistics will be provided

8.1.2.2.2 Objective 2

The safety and tolerability of MK-3866 will be evaluated by clinical assessment of adverse experiences and other safety measurements. Summary statistics for the laboratory safety tests, ECGs, and/or vital signs may also be provided, as deemed clinically appropriate.

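### Does the plan need a prespecified interval for non-renal clearance, given that most of the drug leaves by the kidney?

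*Combined protocol and SAP*

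**What the plan says.** Section 4.2.1 states that "approximately 65% of MK-3866 is excreted in the urine following a single IV dose" and that the hepatic route is "expected to account for the remainder of the non-renal elimination of MK-3866, approximately 35"%. It gives the trial's purpose as learning how HI affects plasma PK "in order to guide dosing recommendations for patients with HI", and says "exposure increases with severe HI are anticipated to be approximately 1.5-fold".

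The primary objectives (Section 3.1) compare plasma PK, with AUC0-inf as the estimated quantity. Secondary objective 1 (Section 3.2) compares CLr and fe. In Section 8.1.2.1 the AUCs, the end-of-infusion concentration and total CL are log-transformed and "evaluated with a linear fixed effects model containing a categorical effect for populations", with a separate variance for each population and 90% intervals for the HI/control ratios. Section 8.1.2.2.1 uses the same model for the urine parameters; a 90% interval "will be calculated for each urine PK parameters (fe and CL_r"). It adds: "Individual values will be listed for each urine PK parameter (fe and CL_r) by population, and non model-based descriptive statistics will be provided".

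Controls are matched on panel-mean age and BMI, with gender counts balanced (Sections 2.1, 5.1.2 and 5.4). Renal function enters only through the eGFR exclusions in Section 5.1.3: at or below 60 mL/min/1.73 m² for controls and moderate HI, at or below 50 for severe HI. CLNR is not defined, listed or compared anywhere.

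**The concern.** If about two thirds of clearance is renal, total CL and AUC mix two routes. The HI panels may have poorer renal function than their controls, because eGFR is neither matched nor a covariate and the severe panel may enrol subjects with eGFR above 50 and up to 60, whom the control criteria exclude. A given AUC ratio could then come from a large hepatic loss, a mixture, or partly from renal imbalance.

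The planned CL and CLr intervals cannot simply be subtracted to give an interval for CLNR, since CLr is part of CL and the two are correlated within subject. A dosing recommendation for HI might then carry a renal component that no planned interval isolates.

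**Working it through.** **Inputs.** Renal and non-renal shares 65% and 35%, and an anticipated AUC ratio of 1.5 in severe HI (Section 4.2.1). Log AUC variance 0.0196 in healthy subjects, "inflated by a factor of 2 for severe hepatic insufficient subjects", so 0.0392; 6 v 6 (Section 8.1.1). Assumed, not in the documents: CLr measurement error CV of 5% to 15%, and between-subject fe spread of 0 or 15%.

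**The plan's own precision.** Half-width = t(0.95, 10 df) × √((0.0196 + 0.0392)/6) = 1.812 × 0.0990 = 0.179 on the log scale, a factor of exp(0.179) = 1.197. This agrees with Section 8.1.1. (The divisor 1.163 printed there for the lower limit does not match the section's own example of 1.25, since 1.5/1.163 = 1.29. That is a separate slip with no bearing here.)

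**Can one AUC ratio hide different routes?** Let r and h be the HI/control ratios of renal and non-renal clearance.

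- AUC ratio = 1/(0.35h + 0.65r)
- fe ratio ≈ r × AUC ratio, if little drug is excreted after 24 h
- CLNR difference = 35 × (h − 1) points of control CL

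With h = 1, r = 50/60 gives 1/0.892 = 1.12 and r = 0.7 gives 1/0.805 = 1.24. The first compares eligibility floors for the severe panel and does not predict means; the second is assumed. For an AUC ratio of 1.5:

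| Route | h | CLNR difference | fe ratio |
|---|---|---|---|
| r = 1 | 0.048 | −33 points | 1.50 |
| r = 0.8 | 0.419 | −20 points | 1.20 |
| r = h = 0.667 | 0.667 | −12 points | 1.00 |

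So AUC alone cannot identify the route.

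**Do the planned intervals identify it?** Simulation at 6 v 6 with the variances above and 90% Welch intervals. Ranges run over the assumed CLr error and fe spread.

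| Route | CL below 1 | CLr below 1 | fe above 1 | CLNR difference excludes 0 |
|---|---|---|---|---|
| r = 1 | 98% | 5% | 92–100% | 97–100% |
| r = 0.8 | 98% | 37–63% | 39–100% | 75–100% |
| r = h = 0.667 | 98% | 76–97% | 5% | 39–94% |

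The 5% entries are the chance rate expected where the true ratio is 1. Because fe is close to CLr/CL in each subject, its interval already allows for the within-subject correlation.

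**What would a CLNR interval add?** Its expected half-width is 5 to 12 points of control CL with no fe spread and 11 to 16 points with 15% spread; coverage is 0.90 to 0.91. The gain is at r = 0.8, and in giving an absolute figure at r = h = 0.667, where fe does not move.

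**What would it cost in bias?** Subtraction counts uncollected urine as non-renal clearance, and Section 7.1.3.2.2 allows for subjects who cannot void at the end of an interval. If 10% of urine were lost in the HI panel only (assumed), the CLNR difference would move toward zero by 0.10 × 65r points: 6.5, 5.2 and 4.3 for the three routes. Coverage of the 90% interval would fall to between 0.34 and 0.85, and detection of the −12 point effect from 39–94% to 22–60%.

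**The case for a change.** The best case for a change is that it is cheap and fills a real gap. CL, CLr, AUC0-24, 24-hour urine and eGFR are all planned, so one SAP paragraph would suffice. An interval whose scale and derivation are chosen after seeing twelve values per comparison is post hoc. At r = 0.8 the planned fe and CLr intervals can both be inconclusive where CLNR would more often exclude zero.

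That gain stands, but it is limited. It occurs in one of the three routes examined, and the same urine error that affects fe and CLr carries into CLNR. The scale is also open to argument. A log ratio would match the rest of the SAP but fails if CLNR is near or below zero, as it could be when h is about 0.05; an untransformed difference avoids this but departs from the ratio framework. Neither is so clearly right that leaving it out is an error.

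The imbalance itself is largely supposition. Panel A and the controls share the same eGFR floor, and the documents give no expected eGFR by panel. Because individual CL, CLr and fe are to be listed and the trial is open-label and estimates without testing, a CLNR summary can be added later without affecting any error rate. Only prespecification is lost.

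**Conclusion.** No change is needed. The population-only model gives a valid estimate of the total HI-versus-control difference in exposure, which is what the primary objectives ask for. The planned CL, CLr and fe comparisons show the route well when clearance loss is purely non-renal or shared equally, and less reliably in between (at r = 0.8, CLr below 1 in 37–63% of runs and fe above 1 in 39–100%).

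An untransformed CLNR difference, with screening eGFR tabulated by panel, would be a sensible optional supplement. It should be read beside fe and CLr, labelled imprecise (about ±5 to ±16 points of control CL) and labelled as overstating CLNR when urine is lost. An interval that includes zero would not show absence of a hepatic effect.

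This conclusion rests on the protocol's 65/35 split, the Section 8.1.1 variances for the severe panel, and the assumed CLr error and fe spread.
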